Aim 2: Pilot testing the effect of the tailored iHBE on fatigue, pain, affective well-being, resilience and BDNF level among low-income cancer survivors living with co-morbid conditions at completion (12 weeks) and 6 months in comparison to usual care waiting list group.

After adjustment in the protocol based on Aim 1, 50 participants who meet the inclusion criteria will be randomly assigned to a 12-week experimental (preferred physical activities) group or a usual care usual care (waiting list) group. Variables will be measured at baseline, completion (12 weeks) and 6 months.

Hypothesis 2: After controlling for the age, gender, race, and BMI, participants in the experimental group will have a greater decline in fatigue, pain, and a greater increase in AWB, resilience and BDNF level from baseline to program completion and 3 months compared to the usual care group.

Aim 3: Examine the association between the changes in the biomarker (BDNF) in serum and sweat after the 12-weeks from baseline and at 3 months post program completion from baseline iBHE program. Hypothesis 3: the change in the serum BDNF level is positively associated with a change in the sweat BDNF level at the after the 12-weeks from baseline and at 6 months from baseline iBHE program.

Sample and Setting:

The study participants will be recruited from the home health care agencies in Baltimore, Maryland, Johns Hopkins Comprehensive Cancer Center and Johns Hopkins Hospital.

Inclusion criteria are (1) participants diagnosed with solid tumor cancer who have completed cancer treatment at least 6 months; (2) diagnosed with diabetes and/or hypertension for at least a year; (3) aged 21 years or older, (4) have an annual household incomes of below \$30,000 for families of three, (5) the average fatigue level within the past 7 days at the level of 3 or more on the 0 (no fatigue) to 10 (worse fatigue) Likert scale and (6) give informed consent.

Exclusion criteria are those (1) currently undergoing treatment for cancer; (2) have an active infection (e.g., fever, localized redness, swelling, sinus congestion); and/or (3) diagnosed with a psychological disorder (e.g., suicidal or homicidal tendencies, extreme anxiety or depression).

Sample size justification

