Phase 2: With an alpha level of .05, the statistical power of 0.80, and 25 participants per group, we will be able to detect significant differences of moderate to large effect sizes of 0.65 when comparing change across baseline, 3-months, and 6-months between the two groups. With an attrition rate of 12% (22 participants per group), the detectable effect size increases to 0.69. Since this is a pilot study and not powered to detect small to moderate effect sizes, we will pay close attention to the effect size, rather than statistical significance. These effect size estimates will be used to inform future research trials.

Date: November 14, 2018

Principal Investigator: [name]

Application Number: IRB00175781

Randomization: Eligible participants will be randomized in a 1:1 allocation ratio to one of the two treatment arms. The electronic Research Electronic Data Capture (REDCap), a randomization application will be used to randomly assigned the participants to the groups

Data Collection Schedule and Procedures. Upon receiving approval from the Johns Hopkins University Institutional Review Board, the study flyer will be posted and distributed at the home health care agencies in Baltimore, Maryland, Johns Hopkins Comprehensive Cancer Center and Johns Hopkins Hospital.

Recruitment, Informed Consent, and Confidentiality. Recruitment methods for this study include (1) distributing and posting flyers, with a tear-off phone number to speak with the principal investigator (PI) as necessary, posted at the hospital (2) face-to-face recruitment for potential participants during cancer support group meetings; and (3) word-of-mouth. Potential participants will receive a verbal explanation by phone or face to face meeting in terms suited to their comprehension of the purpose, procedures, and potential risks of the study. During the screening for eligibility process, an oncologist will be available for consultation. The oncologist will be notified and consulted for the appropriateness of the exercise for participants who self-report having co-morbidities. The participants and family or legal guardian will have an opportunity to carefully review the consent form and ask questions regarding this study prior to signing. Participants will be encouraged to consult with their primary doctor if any concern or an additional question. Participants will be informed that they may withdraw from the study at any time without prejudice to themselves.

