Exclusion criteria are those (1) currently undergoing treatment for cancer; (2) have an active infection (e.g., fever, localized redness, swelling, sinus congestion); and/or (3) diagnosed with a psychological disorder (e.g., suicidal or homicidal tendencies, extreme anxiety or depression).

6. Drugs/Substances/Devices

None

7. Study Statistics

Phase 2 Data analysis

To test **Hypothesis 2 (Aim 2)** examining the effectiveness of iHBE program on fatigue, pain, well-being, resilience and BDNF levels, generalized estimating equations (GEE) will be used. The models will include time as a within-subject fixed effect (baseline, 3 months, 6 months), group (intervention vs usual care) as a fixed-effect between-subject factor and the group by time interaction. Baseline age, race gender, and BMI will be included as covariates. A significant group by time interaction would signify that the change over time in the outcomes differed for the intervention and usual care groups. GEE was selected because it uses all available data and does not require complete data across time for a participant to be included in the analyses. Correlation will be used to test the relationship between the changes in serum and sweat BDNF levels (**Aim 3**). Change from baseline to 3 months and change from baseline to 6 months will be computed for serum BDNF and separately for sweat BDNF. The correlation between the change scores measured by the different modes will be estimated at each time point

8. Risks: Same as phase 1

9. Benefits: Same as phase 1

10. Payment and Remuneration

Date: November 14, 2018

Principal Investigator: [name]

Application Number: IRB00175781

Phase 2 (Aim 2 and 3) - The participants in both the intervention group and the control group will each receive a total of \$80 (\$20 at the start of the intervention, \$30 at the end of the intervention and \$30 at 6 months)

11. Costs

There will be no cost for participants to participate in this study.

12. Data Safety Monitoring Plan

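### Cheap gain in precision, not a validity fault: the group-by-time test compares raw change scores, leaves the baseline outcome unused as a covariate, and is barely touched by the four listed covariates

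*Combined protocol and SAP*

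**What the plan says.** Phase 2, section 7 (Study Statistics) specifies the GEE: "The models will include time as a within-subject fixed effect (baseline, 3 months, 6 months), group (intervention vs usual care"), plus their interaction. Baseline is therefore one level of time, and the baseline outcome is part of the response. The covariate sentence is "Baseline age, race gender, and BMI will be included as covariates". It does not list the baseline outcome, any covariate-by-time term or a common baseline mean for the arms. No link function or working correlation is stated. The test is read as follows: "A significant group by time interaction would signify that the change over time in the outcomes differed for the intervention and usual care groups". The choice of method is justified thus: "GEE was selected because it uses all available data and does not require complete data across time".

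Hypothesis 2 announces the same control: "After controlling for the age, gender, race, and BMI, participants in the experimental group will have a greater decline in fatigue, pain". The sample size justification refers to "effect sizes of 0.65 when comparing change across baseline, 3-months, and 6-months between the two groups" and adds that "we will pay close attention to the effect size, rather than statistical significance".

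**The concern.** A reader of Hypothesis 2 would expect the four covariates to sharpen or protect the treatment comparison. In this layout they do almost nothing to the tested contrast. The baseline value of the same outcome, usually the most useful covariate, enters only by subtraction, with its slope fixed at 1 and not estimated. At stake is interval width. The pilot's main product is an effect-size estimate for planning later trials, and it has 25 participants per arm to obtain one.

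**Working it through.** **Inputs.** From the sample size justification: 25 per arm, 22 after 12% attrition, alpha 0.05, power 0.80, detectable effects 0.65 and 0.69. Assumed because the documents are silent: ρ from 0.3 to 0.8, k from 0.7 to 1.2, identity link.

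**1. The plan's own figure.** A plain two-sided two-sample t comparison at 80% power detects 0.809 SD (25 per arm) or 0.865 SD (22 per arm), not 0.65 and 0.69. Both stated figures return if the variance is multiplied by 0.64: 0.809 × √0.64 = 0.647 and 0.865 × √0.64 = 0.692. That factor arises from a change score with k = 1 and ρ = 0.68, since 2(1−0.68) = 0.64. It also arises from a baseline-adjusted comparison with ρ = 0.6, since 1−0.6² = 0.64. The figures therefore do not show which analysis was assumed, although the wording speaks of change.

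**2. What the planned test estimates.** In one simulated complete dataset (ρ 0.5, exchangeable), the 3-month interaction was 1.0472, identical to the raw difference in mean change. Adding the four covariates left the estimate and the robust SE (0.2338) unchanged. In a dataset with 12% dropout the estimate moved from 1.293 to 1.299 and the SE from 0.3077 to 0.3078.

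**3. Cost of fixing the slope at 1.** In units of 2 × (follow-up SD)²/n:
- change score: 1 + k² − 2kρ
- baseline-adjusted: 1 − ρ²
- difference: (k − ρ)², which is never negative and is zero at k = ρ.

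Example, k = 1 and ρ = 0.5: 0.75/1.00 = 0.75. Adjusted over change variance, before any loss from the other covariates:

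| k | ρ 0.3 | ρ 0.5 | ρ 0.7 | ρ 0.8 |
|---|---|---|---|---|
| 0.7 | 0.85 | 0.95 | 1.00 | 0.97 |
| 0.8 | 0.78 | 0.89 | 0.98 | 1.00 |
| 1.0 | 0.65 | 0.75 | 0.85 | 0.90 |
| 1.2 | 0.53 | 0.60 | 0.67 | 0.69 |

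**4. With the four covariates kept.** Simulated GEE, 25 per arm, complete data, covariates assumed to explain 10% of variance, 6,000 trials per setting. The 95% CI half-width at 3 months in SD, plan v baseline-adjusted:

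| k | ρ 0.3 | ρ 0.5 | ρ 0.7 | ρ 0.8 |
|---|---|---|---|---|
| 1.0 | 0.67 v 0.55 | 0.57 v 0.50 | 0.44 v 0.42 | 0.36 v 0.35 |
| 0.8 | 0.61 v 0.55 | 0.52 v 0.50 | 0.41 v 0.42 | 0.34 v 0.35 |

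A separate simulation of the same layout gave variance ratios of 0.65/0.81/0.92/1.01 at k = 1 and 0.82/0.96/1.07/1.11 at k = 0.8. The last is about 5% in width (√1.11 = 1.05). With a more conservative small-sample SE (Mancl-DeRouen), the gain at k = 1 is gone by ρ = 0.7.

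**5. Tie to the stated 0.65.** Suppose 0.65 is a single-visit change effect in follow-up SDs (an assumption). Then 1+k²−2kρ = (0.65/0.809)² = 0.646, which implies ρ of 0.60, 0.62, 0.68 and 0.75 at k of 0.7, 0.8, 1 and 1.2. Adjustment, before covariate degrees of freedom, moves the detectable effect from 0.65 to about 0.65, 0.63, 0.60 and 0.54.

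**6. Can Phase 1 settle ρ?** No. With 8 participants and an observed 0.5, Fisher's z gives 0.549 ± 1.96/√5, a 95% CI for ρ of −0.32 to 0.89. Phase 1 follow-up is also at 4 weeks, not 12.

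**The case against.** The strongest reply is that nothing here is an error. Group by time in a GEE is a standard analysis, Hypothesis 2 is worded as change from baseline, and the trial is a pilot. The gain rests on two quantities that the documents do not give. For fatigue, entry requires "the average fatigue level within the past 7 days at the level of 3 or more", which may narrow the baseline spread and put k below 1. Step 5 then leaves little or no gain. All of this stands, and it is why the priority is low. The wording of the hypothesis is no obstacle to adjustment, however: once baseline is a covariate, the group difference is the same whether the response is the follow-up value or the change.

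A reader might infer more than the documents support:
- *That the plan ignores baseline or is biased.* Change scores subtract each person's baseline, and randomization makes the comparison unbiased. Simulated mean estimates were 0.64 to 0.67 under every model, for a true 0.65.
- *That the four covariates are pointless.* They cancel only with complete data and an identity link. With strong dropout tied to them in opposite directions by arm (assumed, k = 1), the bias was −0.043 to −0.070 SD without them and about 0 with them.
- *That power rises sharply because both visits gain.* This needs a clean 6-month contrast. The usual-care paragraph places those participants' program after the study ends, while the Phase 2 data collection section places it after the 12-week program.

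**Conclusion.** The point holds as an efficiency suggestion, not as a fault. Baseline adjustment gives a clearly narrower interval at low to moderate ρ with k of 1 or more: at k = 1 and ρ = 0.3, a half-width of 0.55 against 0.67 SD. The gain is small at k = 1 and ρ = 0.7. Where k is near ρ, or ρ is high, it is nil, or the interval is a few percent wider once the four covariates are kept. These figures rest on assumed ρ and k, an identity link, and covariates entered as main effects only, which is the plain reading of the section. It would be wrong to call the change free or certain to help. Priority: optional to low.

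**What to change.** In Phase 2, section 7, keep the GEE and amend the model along these lines:

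> *The 3- and 6-month values will be modelled (identity link) on time, group, group by time, baseline outcome by time, and age, gender, race and BMI. The adjusted group difference will be reported with its 95% CI at 3 and at 6 months, with a joint 2-df test of the two differences.*

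The joint test should replace the sentence that interprets the group-by-time interaction. Once baseline leaves the response, that interaction asks only whether the group difference changes between 3 and 6 months.

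Alternatively, keep all three visits and constrain the arms to a common baseline mean, preferably with visit-specific SDs (for example a mixed model with unstructured covariance). This retains participants who have only a baseline value, in line with the plan's reason for choosing GEE. An exchangeable GEE with a common baseline is also acceptable. At k = 1 its variance relative to the plan was 0.61/0.78/0.89 at ρ 0.3/0.5/0.7, against 0.63/0.85/0.96 with baseline as a covariate. The exception is a baseline SD clearly below the follow-up SD together with high ρ, where its variance was up to 16% above the plan's (k = 0.7, ρ = 0.8).

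Cost: analysis wording, no new data. With baseline as a covariate, participants without any follow-up value contribute nothing. Two reconciliations come first:
- For BDNF, the Phase 2 recruitment section dates the first blood draw to week 1 and the first sweat sample to before the program. The data collection section lists blood, but not sweat, in the assessment before randomization.
- The two statements on when usual-care participants receive the program must agree before the 6-month difference or the joint test is interpreted.

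### GEE is chosen for its use of incomplete data, but with no working correlation or missing-data assumption stated, arm-specific dropout could bias the 6-month effect

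*Combined protocol and SAP*

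**What the plan says.** Phase 2, section 7 (Study Statistics, Phase 2 Data analysis) says that for fatigue, pain, well-being, resilience and BDNF "generalized estimating equations (GEE) will be used". The terms are "time as a within-subject fixed effect (baseline, 3 months, 6 months"), group, and their interaction. "Baseline age, race gender, and BMI will be included as covariates". The one reason given for the method is that "it uses all available data and does not require complete data across time". The section names no working correlation, variance estimator, weighting, imputation, missing-data assumption or sensitivity analysis, and no other section supplies them.

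The Phase 2 sample size justification starts "With an alpha level of .05, the statistical power of 0.80, and 25 participants per group" and gives a detectable effect of 0.65. It continues "With an attrition rate of 12% (22 participants per group"), which raises that figure to 0.69. The same paragraph says that effect size will be weighed above significance and that the estimates will feed later trials.

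**The concern.** Keeping a participant's earlier rows is not the same as estimating the 6-month mean without bias. Whether those rows correct for selective dropout depends on the working correlation. Under independence they do not: each arm's 6-month mean is in effect the mean of those still present. The plan leaves this choice open, and at least one common package (statsmodels) uses independence if nothing is set.

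The plan treats attrition only as lost precision. The pilot's main product is an effect size for planning a later trial, so a shift in the estimate matters more here than a small loss of power. For example, if participants with worse 12-week fatigue left the iHBE arm only, the 6-month effect would look too favourable. The reverse pattern would make it look too small.

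**Working it through.** **The plan's own figures.** 25 × (1 − 0.12) = 22 per group. For a two-sided normal test of a difference averaged over three time points, with an assumed within-person correlation r = 0.5:

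d = (1.960 + 0.842) × √(2/n) × √((1 + 2r)/3)

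- n = 25: 2.802 × 0.283 × 0.816 = 0.647 (stated 0.65)
- n = 22: 2.802 × 0.302 × 0.816 = 0.690 (stated 0.69)

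The figures reproduce, but only with a correlation that the plan does not state. Attrition enters through n alone.

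**Assumptions for the bias.** Scores are in SD units and higher is worse. Baseline and week 12 are complete, and 12% are missing at month 6. Dropout is logistic in the 12-week score y, with slope b = 1 or 2 per SD and an intercept set to give 12% overall. Three correlation patterns are used (baseline–week 12 / baseline–month 6 / week 12–month 6): 0.5/0.5/0.5, 0.6/0.4/0.6 and 0.4/0.3/0.7. None of the slopes or correlations comes from the documents.

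**Bias under working independence, one arm affected.** The 6-month mean of those who stay shifts by

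bias = −ρ × p/(1 − p) × m

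Here ρ is the week 12–month 6 correlation, p = 0.12 (so p/(1 − p) = 0.136), and m is the mean 12-week score of those who leave. Integrating the logistic dropout curve over a standard normal y gives:

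- b = 1: intercept −2.34, m = 0.79
- b = 2: intercept −3.13, m = 1.23

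The two ends of the range are:

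- b = 1, ρ = 0.5: −0.5 × 0.136 × 0.79 = −0.054
- b = 2, ρ = 0.7: −0.7 × 0.136 × 1.23 = −0.117

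If selection runs in opposite directions in the two arms, the shifts add: −0.108 to −0.234.

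**All structures.** Large-sample simulation (400,000 per arm) agrees. Absolute bias in the 6-month effect, in SD, over repeated runs:

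| Dropout pattern | Independence | Exchangeable | Correct unstructured |
|---|---|---|---|
| One arm only | 0.05–0.12 | 0–0.04 | about 0 |
| Opposing arms (worst case) | 0.11–0.24 | 0–0.09 | about 0 |
| Same in both arms | about 0 | about 0 | about 0 |

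**Cross-check at trial size.** A sharper rule removed the 12% of each arm with the most extreme 12-week scores, in opposite directions by arm, with added noise of 0.5 SD. In 300 trials of 25 per arm the bias was −0.18 under independence and 0.00 under exchangeable (Monte Carlo standard error about 0.02).

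**Against sampling error.** With correlation 0.5, the standard error of the 6-month change contrast at 22 per arm is √(2 × (1 − 0.5)) × √(2/22) = 0.30 SD. The one-arm bias is therefore 0.05/0.30 to 0.12/0.30, or about 0.2 to 0.4 of a standard error.

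**Dropout driven by the unseen 6-month value.** With 12% missing and selection on the 6-month score differing by arm, a bias of about 0.13–0.27 SD remains even with the true covariance.

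**Size of the test (a separate matter).** In null simulations with four covariates, the uncorrected robust 2-df Wald test of group by time rejected about 6.5–7.5% of the time at 22–25 per arm, against a nominal 5%.

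**The case against.** The strongest reply is that GEE is not the fault. A reader might infer that GEE is unbiased here only if dropout is completely random. That is too strong. Dropout explained by group, time, age, race, gender or BMI does no harm. For a continuous outcome, GEE with a correct unstructured working correlation performs about as well under missing at random as the likelihood model. The bias comes mainly from working independence, which the plan never says it will use. This stands, and it narrows the point to an unstated structure and an unstated assumption.

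A reader might also infer that the pilot's effect will be overstated. The documents do not support that. They give one attrition rate for both groups and equal payments, including $30 at 6 months in each arm. The contrast is biased only if selection differs by arm. There are grounds for thinking it might: one arm has home visits, calls and exercise while the other has booklets and a wearable, and the Background reports low engagement with home exercise. These make the pattern plausible but are not evidence of it.

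Finally, the one-arm bias is small beside the noise of a pilot, and the Phase 1 text says its results may inform alternative analysis approaches, so the Phase 2 analysis is open to change. Both facts lower the weight of the point. Neither supplies the missing specification.

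**Conclusion.** The concern holds in limited form. The stated reason for GEE does not protect the 6-month estimate from outcome-related dropout that differs by arm, and the plan leaves open the choice that decides how much protection there is. Under the assumed 12% dropout and log-odds of 1–2 per SD, working independence costs about 0.05–0.12 SD with one arm affected. Opposing selection, at 0.11–0.24 SD, is a worst case and not an expectation. The bias is near 0 under equal selection or a correct covariance. The direction cannot be known in advance.

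These sizes rest on assumed correlations and dropout mechanisms, so they are a range and not a prediction. They should not be read as a share of 0.65, which is a detectable effect and not an expected one. This is a cheap improvement to a pilot whose product is an effect size. It does not invalidate the design.

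**What to change.** Make the primary Aim 2 analysis a likelihood-based repeated-measures model with the terms already planned (group, time, group by time, age, race, gender, BMI), unstructured covariance, REML and Kenward-Roger degrees of freedom. State that it assumes data missing at random. With three visits the unstructured covariance has six parameters. The small-sample degrees of freedom also address the inflated interaction test.

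If GEE is kept, name an unstructured or exchangeable working correlation and a small-sample-corrected sandwich variance. Weighted GEE, or multiple imputation that includes the 12-week outcome, would also answer the point.

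In either case, report dropout by arm with reasons, and add a simple missing-not-at-random sensitivity analysis at 6 months, because no model of the observed data cures dropout driven by unseen values.

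The cost is revised analysis wording, slightly more analysis work and slightly wider intervals. No extra data, visits or participants are needed.

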The purpose of this phase 1 pilot study is to examine the feasibility, acceptability and preliminary efficacy of a promising home-based, tailored, technology-enhanced exercise program (iHBE). The intervention is guided by the *Society to Cells* framework and tailors activity based on the individual's preferences, resources, and readiness and it harnesses technology to provide a reminder and immediate feedback on physical performance.(Blaney, Lowe-Strong, Rankin-Watt, Campbell, & Gracey, 2013; Studenski et al., 2010) After pilot testing the feasibility and acceptability of the intervention, we will conduct an RCT to examine the preliminary efficacy of the item on health outcomes (fatigue, pain, AWB, resilience, and BDNF) among low-income cancer survivors living with MCC. We will obtain measures at baseline and 4-week follow-up using a combination of self-report and objective measures. Brain-derived neurotrophic factor (BDNF) is a protein in oxidative stress pathway(Markham et al., 2012) that is related to fatigue(Saligan, Lukkahatai, Holder, Walitt, & Machado-Vieira, 2015) and resilience.(Holmes, 2014) A consistent, light-intensity aerobic exercise can significantly increase 25% of serum BDNF level from baseline.(Zimmer et al., 2017) We propose to examine this biomarker as one of the outcomes to identify the potential biological mechanism of pain, fatigue, and resilience. BDNF testing does not account for circadian rhythm nor temporality to exercise and requires venipuncture. Therefore, a secondary goal of this study is to examine the level of sweat BDNF, non-invasively collected over 72 hours in comparison to serum BDNF. The specific aims of this phase 1 pilot project are to **examine the feasibility and acceptability of the iBHE program among low-income cancer survivors living with co-morbid conditions.** Eight participants who have completed treatment for a solid tumor cancer with at least one comorbidity (e.g., diabetes and/or hypertension) will be assigned to an open-label trial of the iBHE. The feasibility of this first study phase is defined as the acceptability, compliance, and delivery of the intervention. The feasibility of the intervention program will be determined from the achievement of individual physical activity goal. At the end of 4 week program, research team will review the participants ability to achieve at least 75% of the individual's exercise goal (for example, if the goal is to exercise at the fat burn level (50-60% maximum heart rate measured by FitBit) for 30 min/day 3 days week, participants can exercise for 30 min for at least 2 days or FitBit data showed more than 60 active min). For this first phase, at least 50% of participants will need to meet 75% of personal goal in at least 2 weeks for the trial to continue onto phase II. For participants who do not achieve 75% of their individual exercise goal, the barriers will be identified that the weekly goals will be revised until the 75% of weekly personal exercise goals is met. If the feasibility threshold (less than 50% of participants achieve 75% of their weekly goals for 2 weeks) does not reach, we will adjust the goal setting process and recruit more participants. We will conduct a qualitative semi-structured interviews interview to gather feedback on goal setting, problem-solving strategies, exercise choices, and tracking mechanisms, program feasibility, and acceptability and modify the intervention as needed. The descriptive information in this phase I to help inform alternative

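### Aim 3 plans two overlapping change-score correlations with no overall estimate and no analysis of levels; each alone uses about half of the within-person information in three visits, and the two averaged lose about a fifth

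*Combined protocol and SAP*

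**What the plan says.** All references are to the combined protocol and SAP.

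- **Phase 2, section 7 (Study Statistics), Aim 3.** "Correlation will be used to test the relationship between the changes in serum and sweat BDNF levels". The inputs follow: "Change from baseline to 3 months and change from baseline to 6 months will be computed for serum BDNF and separately for sweat BDNF". Then: "The correlation between the change scores measured by the different modes will be estimated at each time point". The type of correlation, the arms included, and any target value or precision are not given.
- **Hypothesis 3 (Objectives; Phase 2 Specific Aims).** A positive association between change in serum and change in sweat BDNF, at 12 weeks and at 6 months from baseline.
- **Section 2, Objectives, purpose paragraph.** Because serum testing needs a blood draw, "a secondary goal of this study is to examine the level of sweat BDNF, non-invasively collected over 72 hours in comparison to serum BDNF". Neither the Phase 1 nor the Phase 2 statistics section contains an analysis of levels across the two fluids.
- **Phase 2, Sample size justification.** It covers only the two-group comparison, with a detectable effect of 0.65 for 25 per group at 80% power and 5% alpha. After dropout: "With an attrition rate of 12% (22 participants per group), the detectable effect size increases to 0.69".
- **Sampling times.** The Phase 2 measurement section has sweat collected at baseline, 12 weeks and 3 months after completion. The Phase 2 recruitment and procedures text has blood at weeks 1 and 12, and sweat at baseline and week 12 only.

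**The concern.** If sweat is to stand in for serum, two questions matter. Do the two fluids move together within a person? Does a person who is high in one tend to be high in the other?

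On the first, the plan gives two imprecise answers that overlap through the baseline and has no rule for bringing them together. They can differ by chance alone. A participant without a usable baseline pair contributes to neither, even with both follow-ups complete. The Aim 2 analysis in the same section was chosen precisely because it tolerates incomplete data.

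On the second, nothing is planned, and change scores cannot answer it. The pilot's estimates are meant to inform later trials, so precision is what is at stake.

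**Working it through.** **Inputs.** From the sample size justification: 25 per group, 12% attrition, 25 × 0.88 = 22 per group, so N = 44 if both arms are used ("Eligible participants will be randomized in a 1:1 allocation ratio to one of the two treatment arms"). From the Aim 3 text: two changes, each from baseline. Assumed, because the documents do not say: two-sided 5% tests, normal data, complete pairs at three visits, deviations independent across visits (relaxed in step 5), and a true within-person correlation of 0.30 for illustration.

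**1. The plan's own figure.** There is none for Aim 3. The 0.65 and 0.69 belong to Aim 2. A plain two-sided two-sample t comparison gives 0.81 and 0.86. The stated values need an unstated within-person correlation, for example about 0.68 for a change score. That does not show them to be wrong, and nothing below depends on them.

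**2. One planned correlation against all three visits.** On the Fisher z scale, the variance is about 1/(N − 3) for one change-score correlation and 1/(2N − 3) for a within-person correlation over three visits.
- N = 44: 1/41 against 1/85, so one correlation carries 41/85 = 48% of the information.
- Standard error at r = 0.30, as (1 − r²) × SE(z): 0.91/√41 = 0.142 and 0.91/√85 = 0.099. Simulation gives about 0.138 and 0.097 to 0.099.
- 95% CI at r = 0.30: 0.00 to 0.55 for one correlation, 0.10 to 0.48 pooled.

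**3. Both planned correlations together.** Two changes from the same baseline correlate 0.5, so the two estimates correlate about 0.5² = 0.25 (simulated 0.24 to 0.26).
- Variance of their average: (1/41) × (1 + 0.25)/2 = 0.0152, against 1/85 = 0.0118 pooled.
- Information kept: 0.0118/0.0152 = 77% (simulated 76 to 80%), so about 20 to 24% is lost.
- Standard error at r = 0.30: about 0.11 for the average, 0.097 pooled.

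**4. Power and chance disagreement at r = 0.30, N = 44** (8,000 simulated trials).

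| Analysis | Power |
|---|---|
| Baseline to 3 months | 51.3% |
| Baseline to 6 months | 52.0% |
| Both significant | 30.4% |
| Average of the two | about 72% |
| Pooled, three visits | 81.0% |

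Exactly one of the two is significant in 51.3 + 52.0 − 2 × 30.4 = 42.5% of trials, although the true value is the same at both times.

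**5. Sensitivity.**
- *One arm only, N = 22.* Fisher z of 0.30 is 0.3095. The pooled estimate has 2 × 22 − 3 = 41, and 0.3095 × √41 = 1.98, so power is about 51%.
- *Serial correlation of 0.5.* Pooled type I error rises to about 6%, which is why a robust or bootstrap interval is advisable. With serial correlation of 0.6, one correlation carries up to 55% of the pooled information.
- *Two sampling times.* There is one change score, nothing to pool, and the 6-month correlation cannot be computed.

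**6. Levels are a separate question.** If the person-level share of variance is s in both fluids, the correlation of levels at a visit is s × (between-person r) + (1 − s) × (within-person r). With within = 0 and between = 0.5, it is 0.15 at s = 0.3 and 0.40 at s = 0.8, while both change correlations are zero.

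**The case against.** The strongest defence is that the plan does what Hypothesis 3 asks: association of change with change, at two named times. That stands, and the two correlations should remain. A shared baseline is inherent in any change from baseline and is not an error.

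A reader might infer that the plan throws away about half of its information. The documents do not support this. Both correlations are reported, and together the two changes span every within-person contrast of three visits. About half is true of each correlation taken singly. For the pair it returns only if levels are added and the between- and within-person correlations are assumed equal, which nothing in the documents establishes.

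Nor is the 30% chance that both tests succeed a fair criticism. No joint criterion is stated, and the sample size section puts effect size ahead of significance.

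Pooling does change the estimand. Months 0 to 3 are the active programme and months 3 to 6 are follow-up, and one Phase 2 section has controls receive the programme after 12 weeks. A common association is therefore not assured. This is a reason to check it and to keep the time-specific results.

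The sentence about levels sits in a paragraph introduced as the purpose of the phase 1 pilot, so its tie to Phase 2 is loose. The same paragraph goes on to the randomised trial, though, and neither phase analyses levels. A person-centred model would not supply this either; it has to be added separately.

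**Conclusion.** The point holds in limited form. Aim 3 lacks an overall within-person estimate and any analysis of levels. Each planned correlation alone uses about half of the within-person information. The pair, averaged, loses about a fifth: standard error about 0.11 against 0.097 at r = 0.30, and power about 72% against 81%. The plan specifies no such average, so in practice the reader would be left with two estimates of standard error about 0.14.

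These sizes rest on N = 44 with both arms pooled, complete pairs at three visits, and little serial correlation. The gain from keeping participants with only two visits has not been quantified. With one arm, even the pooled estimate has only about 51% power at r = 0.30. If only two sampling times exist, the pooling gain disappears. The absence of a levels analysis does not depend on any of this. Classed as a cheap improvement.

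**What to change.** 1. Keep the two change-score correlations as the time-specific results for Hypothesis 3.
2. Add, as the overall Aim 3 summary, one repeated-measures within-person correlation or bivariate mixed model over all three visits. Include visit effects, a visit-interaction check and a robust or bootstrap 95% CI, and use participants with paired samples at any two visits.
3. Add the between-person correlation of sweat and serum levels at each visit, to serve the goal in the Objectives.
4. State whether Aim 3 pools both arms.
5. Reconcile the sampling times: two in the Phase 2 recruitment and procedures text, three in the measurement section and implied by the 6-month change score. The same text places the first blood draw at week 1 and the first sweat sample at baseline, so the intended pairing should be stated.

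The cost is a few lines in the analysis section, one extra model and three descriptive correlations. No samples are needed beyond the three visits that the Aim 3 analysis already presupposes. The downside is the assumption of a common association across visits; the interaction check addresses it, though with limited power at this sample size.
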